Target population: Adults aged over 18 with fibromyalgia according to 2016 revised American College of Rheumatology criteria(Wolfe et al. 2016) who are patients of Oxford University Hospitals NHS Foundation Trust or Connect Health community musculoskeletal health, and who have concomitant sleep disturbance (measured used 2- item Sleep Conditions Indicator, SCI-2)	Analysis set: All randomised participants. Participants assigned to dCBT-I and sleep hygiene advice will be the active treatment group. Participants assigned to the sleep hygiene only group will be the comparator group.
Variable: Fibromyalgia-related quality of life measured on the Fibromyalgia Impact Questionnaire Revised (FIQR) at 3-months post- randomisation	Outcome measure: Continuous outcome scale where higher scores indicate worse quality of life, at 3-months post-randomisation
Handling of intercurrent events	Handling of missing data
 Premature treatment discontinuation/non- engagement: All follow-up will be included regardless of attribution to treatment under a treatment policy strategy. Switching Treatment arm: Participants who receive a different intervention to that which they were allocated will be analysed according to their randomised allocation under a principal stratum 	Multilevel modelling of outcome scores over time imputes implicitly intermittent missing data over the post-randomisation period of follow-up. The underlying assumption is missing at random (MAR) conditional on all other outcome scores and minimisation factors. This is the main approach to handling missing data. Sensitivity analysis: The MAR assumption can be strengthened by conditioning on additional baseline covariates predictive of the outcome and
strategy	missingness.
	Missing data arising from participants discontinuing in the study prior to the end of follow-up under a NMAR (Not Missing at random) informative missing data mechanism will be explored using the extended Hausman-Wise-Diggle-Kenward selection model when drop out depends on outcome scores prior to drop out and where this is jointly modelled with the longitudinal outcome(Diggle and Kenward 1994).
Population-level summary measure	Analysis approach
Average Treatment effect (ATE): Mean difference in fibromyalgia-related quality of life scores at 3	Primary analysis: Constrained Longitudinal Data Analysis (cLDA) – The primary analysis will use a Constrained Longitudinal Data Analysis (cLDA) model to estimate the treatment effect of

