3.3 Sample Size

In the pilot phase (phase 1), the mean FIQR at baseline was 57.69 (SD=18.69). At the 3-month post-treatment follow-up, for the overall group, the mean FIQR was 52.24 (SD=19.06). The correlation between baseline and 3-month follow-up FIQR scores was high (r=0.86; 95%CI 0.73 to 0.93).

Using these values, the sample size was estimated to detect a minimum clinically-important difference (MCID) of 14% improvement in FIQR at 3 months (Bennett, Bushmakin, et al. 2009), corresponding to an improvement of 8.08 (Cohen's d=0.43) in this study, equating to a moderate effect size. Assuming a correlation of r=0.75 (the lower bound of the 95% CI for correlation), significance level of 0.05 and 80% power, the estimated sample size required to detect a 14% improvement in FIQR amongst participants in the Sleepio arm compared to the standard care arm using an ANCOVA is 78 participants (39 per group). This calculation includes an adjustment for a 3.33% loss-to-follow-up rate.

The R code used to estimate the sample size is provided below:

```

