3.7 Statistical Analysis Outline

It is anticipated that all the statistical analysis will be undertaken using R although other well-validated statistical packages, such as Stata, may be considered for statistical quality control validation analyses. All analyses will be carried out under a treatment policy strategy (that is, all participants will be analysed in the group they were randomised to regardless of actual treatment received).

The analyses will be repeated for the *per protocol* population (definition in section 4.2) as mandated by the protocol, bearing in mind that this may introduce bias by losing the benefits of randomisation and introducing ambiguity in the primary estimand of interest.

Although we have allowed for up to 5% missing data in the sample size at 3 months, we hope to minimise this by utilising data collection techniques appropriate to the fibromyalgia patient population. Before carrying out the within trial analysis, we will check the trial data for any missing data. Where possible the reasons for missing data will be ascertained and reported. The nature and pattern of the 'missingness' will be carefully considered — including whether data can be treated as missing at random (MAR). The handling missing data is detailed in section 6.3. Standard descriptive statistics will be used to describe the demographics between the treatment groups reporting means and standard deviations or medians and interquartile ranges as appropriate for continuous variables, and numbers and percentages for binary and categorical variables. All comparative outcomes will be presented as summary statistics and reported together with 95% confidence intervals and all tests will be carried out at a 5% two-sided significance level.

The Fibromyalgia Impact Questionnaire Revised (FIQR) at 3 months is the primary outcome of the study and the primary analysis will compare this between the treatment groups in a linear mixed effects method including all participant data, adjusting for the stratification factors.

Subgroups analyses will be undertaken with the aim of exploring the consistency of treatment effects across important baseline characteristics (Yusuf et al. 1991). These include:

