5.5 Treatment Compliance with Details of Intervention

The intervention groups in this trial are dCBT-I and sleep hygiene advice, or sleep hygiene advice only, in adults with fibromyalgia. All participants will be given sleep hygiene advice at the baseline visit. Compliance for dCBT-I is defined by the proportion of participants who complete each of the 6 sessions of dCBT-I. A complier will be defined as a participant who completes at least 3 of the 6 sessions, as session #3 contains sleep restriction therapy, the core component of CBT-I. The numbers and percentages of participants receiving each treatment are summarised, as well as those who did not receive the allocated treatment. Reasons are given in the cases where the participants did not receive the allocated treatment (**Table 5a**). The numbers and percentages of participants in the dCBT-I arm who access, and complete, each session are summarised (**Table 5b**).

Treatment received	dCBT-I and sleep	hygiene	Sleep hygiene only	
	N	%	N	%
Allocated treatment				
Other				
Reason for not receiving allocated treatment				
Participant decision				
Administrative decision				
Other				

Table 5a. Compliance with allocated intervention

Table 5b. Compliance with dCBT-I among intervention group

	Session	Accessed session	Completed session
--	---------	------------------	-------------------

	N	%	N	%
Session 1				
Session 2				
Session 3				
Session 4				
Session 5				
Session 6				

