6.3 Missing Data

Missing data will be minimised by careful data management. Missing data will be described with reasons given where available; the number and percentage of individuals in the missing category will be presented by treatment arm. No data will be considered spurious in the analysis since all data will be checked and cleaned before analysis.

Missing covariate data: If the amount of missing covariate data leads to exclusion of less than 5% of participants, and it is implausible that such exclusion is associated with outcomes or is not associated with observed outcomes, then missing data will be considered ignorable. Fully adjusted analyses will be based on all randomised participants using imputed covariate data using single conditional imputation. Sensitivity analyses will include adjusted analyses based on those with complete covariate profile.

If the amount of missing covariate data leads to exclusion of more than 5% of participants, and auxiliary variables can be identified that are associated with missingness with predictive value for the missing data, then multiple imputation will be employed, including observed outcomes, randomised treatment, auxiliary covariate data predictive of missingness and all variables which will be used in adjusted analyses. The imputation model will include all participants randomised in the group originally assigned.

Missing outcome data: The primary analysis method proposed is reasonably robust to missing at random (MAR) data conditional on all outcome measurements on all other visits and other covariates included in the model (**Table 1**). To address missing data, a multilevel mixed-effects model (cLDA) will be used, which implicitly accounts for intermittent missing data under the MAR assumption(Lu 2010).

Drop-out indicators will be created and we will report the counts of participants dropping out by arm, as well as the follow-up visit they dropped out of (**Table 3a**). For the purpose of our main analyses reporting outcomes up to 6 months, we consider a participant as having drop-out at a particular visit if all follow-up outcome assessments following that visit are all missing.

We will then examine any association of drop-out with important prognostic factors such as age, sex, education level, depression (PHQ-9), anxiety (GAD-7), and clinically significant SAEs relating to the interventions (Section 6.7), and baseline FIQR scores as well as follow-up FIQR scores observed before drop out.

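### Non-engagers are in the treatment-policy estimand, but no missing-data model uses Sleepio sessions completed, so the 3-month FIQR difference may favour Sleepio if loss follows non-engagement

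*SAP*

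**What the plan says.** Table 1 (SAP section 2) treats early discontinuation and non-engagement as follows: "All follow-up will be included regardless of attribution to treatment under a treatment policy strategy". The target therefore includes the FIQR scores of people who stop using Sleepio.

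For missing scores, the same table says: "The underlying assumption is missing at random (MAR) conditional on all other outcome scores and minimisation factors". (SAP 3.2 describes stratified blocks, so I read the last words as the stratification factors.) The next step is: "The MAR assumption can be strengthened by conditioning on additional baseline covariates predictive of the outcome" and of missingness. SAP 6.2 puts this into practice. The primary cLDA holds time, treatment by time, sex and MRI participation, and the secondary model adds age, PHQ-9 and GAD-7.

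Engagement is measured. SAP 5.5 states: "The numbers and percentages of participants in the dCBT-I arm who access, and complete, each session are summarised". SAP 6.4 uses sessions for the CACE and dose-response analyses. SAP 6.3 plans a drop-out analysis: "We will then examine any association of drop-out with important prognostic factors such as age, sex, education level", followed by depression, anxiety, intervention-related SAEs, and baseline and earlier follow-up FIQR. Sessions completed are not named.

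The plan does not stop at MAR. Table 1 names a selection model for informative drop-out. SAP 6.4 announces two not-at-random approaches and sets out one: delta-adjusted imputation at +1 SD, 0 and -1 SD of observed FIQR.

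**The concern.** A participant lost before month 3 who never returns has only a baseline FIQR. The model then predicts that person's 3-month score from same-arm participants with similar baseline FIQR and strata, whatever their engagement. A lost Sleepio non-engager is implicitly given the benefit seen, on average, in the Sleepio participants who were followed.

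This sits badly with the rest of the SAP. Section 5.5 treats session 3 as holding the core of the therapy. The CACE analysis in 6.4 assumes that allocation affects FIQR only through compliance, so non-compliers gain nothing from it. The variable that the SAP treats as driving benefit is absent from the model that stands in for missing outcomes.

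In a self-directed digital programme, stopping the sessions and stopping the questionnaires could well go together. If so, the estimate drifts from the treatment-policy effect towards the effect in engagers. Adding more baseline covariates would not remove the drift unless they predicted engagement.

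**Working it through.** **The plan's own figure.** SAP 3.3 gives baseline mean 57.69, SD 18.69, r = 0.75, loss 3.3% and "significance level of 0.05 and 80% power". The target is 0.14 × 57.69 = 8.08 points, d = 0.432. Per arm: 2 × (1.96 + 0.842)² / 0.432² = 84.03, rounded up to 85. Then 85 × (1 − 0.75²) = 37.19; 37.19 / 0.967 = 38.46, rounded up to 39; total 78. This reproduces exactly. The standard error of the adjusted difference with 37.19 per arm is 18.69 × √(1 − 0.75²) × √(2/37.19) = 2.87.

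**Assumptions, because the documents give no figures.** Share engaging p = 0.6. Gain in engagers E = 8.08 or 13.5 points; gain in non-engagers 0. The true randomised difference is pE = 4.85 or 8.10. A fraction f of the Sleepio arm is lost before month 3 and does not return. Control loss is taken as unrelated to outcome given baseline.

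**Case A: all lost Sleepio participants are non-engagers.** The observed engager share is p/(1 − f), so bias = pE × f/(1 − f).

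**Case B: non-engagers are four times as likely to be lost.** With engager loss q, f = 0.6q + 0.4 × 4q = 2.2q. Bias = pE × (f − q)/(1 − f), which is (1 − 1/2.2) = 0.545 times case A.

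**Case C: loss unrelated to engagement.** Then q = f and the bias is zero.

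| Sleepio-arm loss f | A, E = 8.08 | A, E = 13.5 | B, E = 8.08 | B, E = 13.5 |
|---|---|---|---|---|
| 3.3% | 0.17 | 0.28 | 0.09 | 0.15 |
| 5% | 0.26 | 0.43 | 0.14 | 0.23 |
| 10% | 0.54 | 0.90 | 0.29 | 0.49 |

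All entries are FIQR points in Sleepio's favour. The formula gives 0.09 to 0.43 at 3.3% to 5%. Simulation at 5% Sleepio-arm loss gave about 0.2 to 0.5, so I quote 0.1 to 0.5 overall.

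**Does the remedy work?** In that simulation, multiple imputation by arm with sessions completed cut the bias to about 0.1, with an SD of the estimate of about 3.1 with or without it. This result is partly built in, because engagement was made the driver of both gain and loss.

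**Do the planned not-at-random analyses cover it?**
- Table 1 describes the selection model as drop-out depending on scores before drop-out. If those scores are observed, that is MAR again, and 6.4 does not carry the model forward.
- A common delta shifts the difference by delta × (Sleepio loss − control loss). With equal loss by arm the shift is zero.
- A Sleepio-only delta of +1 SD (19.06, the pilot 3-month SD) would shift it by 19.06 × 0.033 = 0.63 or 19.06 × 0.05 = 0.95 points. That exceeds the biases above at those loss rates, but no such version is stated.
- SAP 6.1 says that higher FIQR is worse. Yet 6.4 labels +1 SD as optimistic and −1 SD as pessimistic, which is reversed.

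**The case against.** The best defence is that the effect is small and conditional, and that the plan already looks beyond MAR. Much of this stands. At 5% loss about four of 78 people are missing, and a bias of at most about 0.5 points is minor beside a standard error near 3. It arises only if loss follows non-engagement and non-engagers do worse given baseline FIQR; the documents establish neither. Participants missing only month 3 are also informed by their later scores. The list of drop-out predictors in 6.3 is introduced as examples, so sessions could be added without contradiction.

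Three stronger readings are tempting and not supported:
- **That the bias is 0.6 to 0.9 points at the SAP's own loss rates.** This puts the whole trial's 3.3% or 5% loss on Sleepio non-engagers, which is about 6.7% or 10% of that arm, with no control loss. The SAP states no loss by arm.
- **That sessions are the only post-baseline fact known about a lost participant.** SAP 6.3 also lists intervention-related SAEs and earlier follow-up FIQR, Table 3b records withdrawal reasons, and protocol 7.4 requires a daily sleep diary during the programme.
- **That the baseline-covariate model is the only sensitivity analysis.** It is not. The fault is that the others, as worded, do not clearly address this mechanism.

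On the other side, 3.33% equals one in 30, the planned pilot size. If that is its source, the exact 95% upper limit is about 17%, so low loss is not assured.

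**Conclusion.** The gap is real. The estimand counts non-engagers, and neither the primary MAR model nor its strengthened form conditions on engagement, although engagement is recorded. The result may be biased towards Sleepio if loss follows non-engagement and non-engagers gain less; the documents do not show that it will be.

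Under the assumptions above, the size is about 0.1 to 0.5 points at 3.3% to 5% Sleepio-arm loss and about 0.3 to 0.9 at 10%, that is, up to about 11% of the 8.08-point target (0.90 / 8.08). This does not undermine the primary analysis. It justifies one well-aimed sensitivity analysis, because the planned ones could leave a reader unable to tell whether this mechanism matters.

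**What to change.** Keep the primary cLDA and the covariate-adjusted secondary analysis in 6.2. Then:

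1. In Table 1 and 6.4, add multiple imputation of 3- and 6-month FIQR, done separately by arm. Use baseline FIQR, the stratification factors, age, PHQ-9 and GAD-7, plus sessions completed in the dCBT-I arm (0 to 6, or under 3 versus 3 or more if sparse). Fit the same as-randomised cLDA, without sessions in the analysis model, and report it beside the primary result.
2. In 6.3, add sessions completed to the drop-out predictors.
3. In 6.4, also apply delta to the dCBT-I arm alone, and correct the optimistic and pessimistic labels.

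The cost is SAP wording and one imputation analysis on data already held; the sample size does not change. Precision falls slightly when few non-engagers are observed. Bias remains if lost non-engagers differ from retained ones, which is why the Sleepio-only delta is needed as well.

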3. STUDY METHODS

3.1 Trial Design/framework

PainLESS is a single-centre, prospective, randomised, superiority trial using a two-arm parallel group design in a single-centre in Oxford, UK. Adults aged 18 years or older with fibromyalgia and concomitant sleep disturbance, will be randomised in a 1:1 ratio to either receive dCBT-I and sleep hygiene advice, or sleep hygiene advice only. The nature of the treatment means that the participants cannot be blinded to the treatment received; however, the outcome assessors will be blinded to the participant's treatment allocation. This trial was nested within a larger observational cohort. Within the trial, a subgroup of eligible participants underwent a brain MRI at baseline and at 3-months post-randomisation.

The trial includes an internal pilot (phase 1) which was designed to confirm the expected rate of recruitment and feasibility of the study design, and to estimate variability of the outcome measure to inform the sample size for Phase 2. This pilot was planned to include 30 participants. The study investigators will make a decision regarding trial continuation in the event that the recruitment target for the internal pilot is not met. Otherwise, the trial would continue into the main phase (phase 2), and patients from the internal pilot would be included in the final analysis. The main trial phase was planned to be recruiting from Oxford University Hospitals NHS Foundation Trust (OUH) and Connect Health, stratified by sex to account for known imbalances in fibromyalgia prevalence, and by participation in the brain MRI sub-study to ensure a balanced sample for this sub-study. Follow-up was planned to be made in person at 3 months, and electronically (sent by e-mail or text message) for patient reported outcomes at 3 months (primary outcome time-point), 6 months and 12 months.

All adults aged 18 years or older with a diagnosis of fibromyalgia, who are patients of OUH or Connect Health, who have concomitant self-reported sleep disturbance (SCI-2) and brain fog, and who had access to a device with an internet connection humerus are potentially eligible to take part in the trial. Participants with a major neuropsychiatric condition (not including depression or anxiety), neurodegenerative disorder, epilepsy, recent surgery, regular nightshift work, regular use of sedative medications, an untreated sleep disorder apart from insomnia (e.g. obstructive sleep apnoea), who are pregnant or breastfeeding, or who are currently using psychological therapies for insomnia are not eligible. After consent has been gained, an online survey will collect baseline demographic data, fibromyalgia-related quality of life (FIQR), sleep quality (ISI), brain fog (BC-CCI), fear of movement (TSK), pain (SF-36), and health-related quality of life using the EuroQoL EQ-5DY. At a site visit, a trial investigator will collect information on sleep (actigraphy and sleep diary), cognitive performance, physical activity, pain (QST), and brain MRI.

3.2 Randomisation and Blinding

Patients will be randomised after consent and collection of baseline data. Participants will be randomised on a 1:1 basis using *Sealed Envelope*, a secure electronic randomisation platform. To ensure balanced group allocation, randomisation will be stratified by sex and completion of a brain MRI in the neuroimaging sub study, with participants assigned in blocks of 10. Outcome assessors will be blinded to treatment allocation for all study visits and communications with participants, and investigators carrying out analysis will also be blinded. Due to the nature of the intervention, participants were unable to be blinded.

To maintain allocation concealment, all study investigators will not have access to future group allocations and are unable to influence randomisation. The treatment allocation will be communicated to participants by an independent research nurse who is not involved in study visits or outcome assessments via email. This email will consist of scripted phrases and contained instructions for *Sleepio* access. In addition, the research nurse will act as an intermediary for any queries regarding the treatment or group allocation, and will relay questions regarding the intervention to the investigators anonymously to preserve blinding.

Due to the nature of the intervention, blinding participants was not possible. However, the outcome assessors will remain blinded to treatment allocation throughout the trial. Participants were instructed not to disclose their group assignment to study investigators during follow-up visits to maintain blinding. Participants cannot be blinded to their treatment. The outcome data will be collected directly from the participant. Outcome assessors will be blinded to the participant's treatment allocation.

Full details of the randomisation are available in se_list_242996464514928final, stored in the confidential statistical section of the TMF. No emergency randomisation plan was developed for this study.

3.3 Sample Size

In the pilot phase (phase 1), the mean FIQR at baseline was 57.69 (SD=18.69). At the 3-month post-treatment follow-up, for the overall group, the mean FIQR was 52.24 (SD=19.06). The correlation between baseline and 3-month follow-up FIQR scores was high (r=0.86; 95%CI 0.73 to 0.93).

Using these values, the sample size was estimated to detect a minimum clinically-important difference (MCID) of 14% improvement in FIQR at 3 months (Bennett, Bushmakin, et al. 2009), corresponding to an improvement of 8.08 (Cohen's d=0.43) in this study, equating to a moderate effect size. Assuming a correlation of r=0.75 (the lower bound of the 95% CI for correlation), significance level of 0.05 and 80% power, the estimated sample size required to detect a 14% improvement in FIQR amongst participants in the Sleepio arm compared to the standard care arm using an ANCOVA is 78 participants (39 per group). This calculation includes an adjustment for a 3.33% loss-to-follow-up rate.

The R code used to estimate the sample size is provided below:

```
